#### Minnesota Living With Heart Failure (MLWHF)

The mean improvement in MLWHF between baseline and 12 months by treatment arm will be presented with means and confidence intervals using a regression model of change from baseline with covariates for randomization group and baseline value. A generalized estimating equation (GEE) repeated measures model with a compound symmetry working correlation will be used to account for within

subject correlation over time and to estimate the difference between the randomized arms over 12 months of follow-up, adjusted for baseline.

**Rationale:** Improving symptoms is important to patients, particularly an improvement in Quality of Life. Previously, a clinically and statistically significant symptomatic improvement was established at six months for QOL. This endpoint will evaluate the long term, sustainability of an improvement in QoL between the treatment arms.

#### **NT-proBNP**

The mean improvement in NT-proBNP between baseline and 12 months by treatment arm will be presented with means and confidence intervals using a regression model on the log transformed NT proBNP change from baseline with covariates for randomization group and baseline value. A generalized estimating equation (GEE) repeated measures model with a compound symmetry working correlation will be used to account for within subject correlation over time and to estimate the difference between the randomized arms over all times at which the endpoint is collected, adjusted for baseline.

**Rationale:** An improvement in NT-proBNP is associated with a decreased risk of morbidity and mortality events. Previously, a clinically and statistically significant relative reduction in NT-proBNP was established at six months. This analysis will evaluate the long term, up to 12 months, sustainability of a relative reduction in NT-proBNP between the treatment arms.

## **4. SENSITIVITY ANALYSES FOR MORBIDITY AND MORTALITY ENDPOINTS**

The morbidity and mortality sensitivity analysis defined in this SAP includes, and supersedes, the morbidity and mortality sensitivity analysis defined in the main Statistical Analysis Plan (360050-001). These sensitivity analyses will be performed on the primary endpoint, and may also be performed, as appropriate, on the secondary and ancillary endpoints.

### **4.1. Sensitivity Analyses Due to Additional Therapeutic Interventions**

Progression of heart failure may result in additional therapeutic intervention, as defined in Table 3 below, leading to potential bias in the assessment of between arm differences. In order to assess the potential impact of adoption of more intensive therapeutic intervention on the estimation of treatment effect for the morbidity and mortality endpoint, sensitivity analyses will be conducted. These sensitivity analyses acknowledge the potential bias introduced by use of a more intensive therapeutic intervention and serve to assess the degree of bias.

**Table 3: Additional Therapeutic Intervention Sensitivity Analyses**

#	Therapeutic Intervention	Definition
1	New medication class	Intervention is defined as addition of a new class of medication (e.g., ARNI or ivabridine) not part of a subject's baseline medication regimen. ARNI and ivabridine are new medications becoming available for the treatment of heart failure patients at the time of study initiation. Increasing adoption of these medications, or other novel classes of medication yet to be developed, has the potential to impact estimation of the device treatment effect relative to medical management.
2	Medication dose increase	A qualifying medication increase is defined as a 100% increase in the effective dose of medications within a specific drug class (e.g., ACE inhibitors, beta-blockers, etc.) compared to baseline dose for any class of medication that is part of a subject's baseline medication regimen.
3	Cardiac resynchronization therapy (CRT)	Intervention is defined as the addition of a CRT LV lead or the implantation of a CRT device.
4	CardioMEMS device	Intervention is defined as the implantation of a CardioMEMS device. An additional analysis will be performed based on first intervention due to CardioMEMS usage if information available.
5	BAROSTIM NEO device	Intervention is defined as non-protocol implantation of a BAROSTIM NEO device
6	Any intervention (1-5 above)	Overall assessment of sensitivity to any of the specified interventions.
7	Medication class or dose (1-2 above)	Overall assessment of sensitivity to specified medication changes.
8	Device interventions (3-5 above)	Overall assessment of sensitivity to specified device interventions.

The sensitivity analyses defined below will be performed for each of the additional therapeutic interventions in Table 3:

- An analysis will be performed with follow-up censored at the earliest time that a specified therapeutic intervention occurs. For this sensitivity analyses, the earliest occurrence of the specified therapeutic intervention will NOT be considered an event contributing toward the endpoint.
- An analysis will be performed that treats a specified therapeutic intervention as a terminal event (i.e., no other follow-up time or events past the therapeutic intervention will count). For this sensitivity analyses, these terminal events will be considered as an event contributing toward the endpoint.
- An analysis that counts all specified therapeutic interventions as events contributing toward the endpoint, with follow-up time accruing until last available contact/death.
- An analysis imputing events for the post-therapeutic intervention period, separately for the randomized arms. Imputation will be based on subject's baseline covariates and pre-therapeutic intervention data and the amount of follow-up time available post-therapeutic intervention. For this sensitivity analyses, these imputed events will be considered as an event contributing toward the endpoint.

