### 3.3. Eligibility Criteria

#### 3.3.1. Inclusion Criteria

To be eligible for this trial, subjects must meet all of the following inclusion criteria:

1. Age 21 years or above.
2. Currently NYHA Class II or III heart failure. For NYHA Class II, must have been NYHA Class III at any point in time within 3 calendar months prior to enrollment or at time of screening (enrollment is defined as the date the subject provided written consent).
3. Left ventricular ejection fraction  $\leq$  35% within 45 days prior to randomization.
4. Heart failure accompanied by either:
  - Core lab NT-proBNP  $\geq$  400 AND  $<$ 1600 pg/ml within 45 days prior to randomization **OR**
  - Core lab NT-proBNP  $<$  400 pg/ml within 45 days prior to randomization AND a heart failure hospitalization in the past 12 months.

**Note:** Heart failure hospitalization may include an overnight hospital or hospital-based observation unit stay with a primary diagnosis of heart failure or an emergency room visit with a primary diagnosis of heart failure.

**Note:** Screening/Baseline core lab NT-proBNP must be collected in an outpatient setting at a time when the subject is thought to be clinically stable.

5. On optimal, stable, Guideline Directed Medical Therapy (GDMT) per country specific guidelines for the treatment of heart-failure throughout screening/baseline evaluation and for at least 4 weeks prior to obtaining any post-consent screening parameters:
  - No more than a 100% increase or a 50% decrease of the dosage of any one medication other than a diuretic.
  - Medication changes within a drug class are allowed as long as the equivalent dosage is within the limits specified above.
  - Unrestricted changes in diuretics are allowed as long as the subject remains on a diuretic.
6. Six-minute hall walk (6MHW)  $\geq$  150 m AND  $\leq$  400 m within 45 days prior to randomization.

7. The artery planned for the BAROSTIM implant must meet both of the following criteria:
  - At least one carotid bifurcation as identification by a bilateral carotid duplex ultrasound within 6 months prior to randomization that is:
    - a. Below the level of the mandible AND
    - b. No ulcerative carotid arterial plaques AND
    - c. No carotid atherosclerosis producing a 50% or greater reduction in linear diameter in the internal carotid AND
    - d. No carotid atherosclerosis producing a 50% or greater reduction in linear diameter in the distal common carotid

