##### **Heart Failure Hospitalization**

A heart failure hospitalization for worsening heart failure is defined as a non-elective hospitalization that includes at least two of the following: Increased signs (e.g., Jugular venous distention, pulmonary rales, S3, edema), symptoms (e.g., dyspnea on exertion, paroxysmal nocturnal dyspnea, orthopnea, fatigue) or laboratory evidence [e.g., Chest x-ray - PVR, interstitial edema, effusions, significantly increased BNP, NT-proBNP, new onset or worsening prerenal azotemia (BUN/CR)] of worsening heart failure. The administration or augmentation of parenteral agents (e.g., inotropes, diuretics, and/or vasodilators), mechanical heart failure therapy or use of ultrafiltration and/or paracentesis is required.

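### Read literally, the medication rows of SAP Table 3 take in diuretic increases and short-term treatment of decompensation, so these sensitivity analyses can stop follow-up at, or count twice, the outcome they are meant to test

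*SAP*

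**What the plan says.** SAP 4.1, Table 3, defines two kinds of medication intervention. Row 1 is the "addition of a new class of medication (e.g., ARNI or ivabridine) not part of a subject's baseline medication regimen". Row 2 reads "A qualifying medication increase is defined as a 100% increase in the effective dose of medications within a specific drug class", measured against the baseline dose "for any class of medication that is part of a subject's baseline medication regimen". Row 6 (any intervention) and row 7 (any medication change) inherit both, and the last tier of the win ratio in SAP 5.6 refers to Table 3. Neither row mentions diuretics, route, duration, or whether the drug was given during an endpoint event.

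Four analyses follow for each row:
- The first censors follow-up at the earliest intervention and does not count the intervention.
- The second treats the intervention as a terminal event and counts it.
- The third is "An analysis that counts all specified therapeutic interventions as events contributing toward the endpoint", with follow-up continuing.
- The fourth imputes events after the intervention.

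Protocol 4.3.4 makes treatment part of the definition of a heart failure hospitalization: "The administration or augmentation of parenteral agents (e.g., inotropes, diuretics, and/or vasodilators), mechanical heart failure therapy", ultrafiltration or paracentesis must have been used.

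Protocol 3.3.1, inclusion criterion 5, uses the same 100% threshold but exempts diuretics: "No more than a 100% increase or a 50% decrease of the dosage of any one medication other than a diuretic", and "Unrestricted changes in diuretics are allowed as long as the subject remains on a diuretic".

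**The concern.** Table 3 is aimed at background therapy that could mask or mimic a device effect; the named examples are ARNI and ivabradine. A diuretic doubled because the patient is decompensating, or an inotrope or vasodilator started on admission, is part of the outcome. The wording does not separate the two.

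If such changes are scored, the censoring and terminal-event analyses end follow-up when the patient is worsening. That removes recurrent events, which are central to the primary negative binomial analysis, and makes the stopping time outcome-related. SAP 5.3 itself recognises dependent censoring as a problem for the recurrent-event estimate. The event-counting analyses can score an admission once as a hospitalization and again as its own treatment. Either result says less about whether new background therapy explains the device effect. Treatment is also not blinded, so the staff who change a diuretic know the arm.

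**Working it through.** **Check of the wording**

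| Question | SAP Table 3, rows 1 and 2 | Elsewhere in the plan |
|---|---|---|
| Are diuretics excepted? | No; they fall in by wording and are not named | Inclusion criterion 5 excepts them from the same 100% limit |
| Is short-term or parenteral treatment excepted? | No | Protocol 4.3.4 counts parenteral treatment towards the endpoint |
| Is the same care treated as outcome? | No; it can be an intervention | SAP 3.2.2 has a tier for clinic visits with intravenous diuretic; SAP 7 lists acute medication changes among alternative heart failure definitions |
| Is there a rule against counting twice? | None in SAP 4.1 | None found |

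So a doubled diuretic can meet row 2, and a new inotrope or vasodilator can meet row 1, through the treatment of an endpoint event.

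**Do such changes reach the data?** Protocol 3.4.7 collects prescribed heart failure drugs at scheduled visits and does not mention in-hospital doses. Protocol 3.4.11.1 has sites ask about medication changes at each visit. Section F of the COVID form (SAP 9) sends even brief changes to the medication record. An oral diuretic doubling is therefore likely to be captured; an in-hospital infusion may not be.

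**Size.** The plan gives no figure to reproduce, so this is an illustration.

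Inputs: 320 events (SAP 2), 331 subjects, dispersion 1.7 and terminal fraction 0.18 (SAP 8.1). SAP Table 4 labels 1.4 as large overdispersion, so 1.7 is read as a shape parameter k; the reciprocal is run as well.

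*Events lost if follow-up stops at every first event and that event still counts.* Mean per subject m = 320/331 = 0.967. P(no event) = (k/(k+m))^k.
- k = 1.7: P(no event) = 0.465; first events = 331 × 0.535 = 177; lost = 320 − 177 = 143 (45%).
- k = 1/1.7: P(no event) = 0.565; first events = 331 × 0.4355 = 144; lost = 320 − 144 = 176 (55%).

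With the updated 319 subjects (m = 320/319 = 1.003), the same formula gives 146 and 179 (46% and 56%).

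*Double counting.* Non-terminal events = 0.82 × 320 = 262; terminal events = 0.18 × 320 = 57.6.

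| Share of non-terminal events also scored as an intervention | Total | Terminal share |
|---|---|---|
| 25% | 320 + 66 = 386 | 15% |
| 50% | 320 + 131 = 451 | 13% |
| 100% | 320 + 262 = 582 | 10% |

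*Effect on the rate ratio.* Gamma-Poisson simulation with 331 subjects, control rate 0.4, true ratio 0.65, 18% terminal events and 300 runs per setting. Two inputs are assumptions: 3.5 years of maximum follow-up, chosen to give roughly 300 to 325 events, and the share s of non-terminal events with a qualifying drug change. Ratios are crude (events over time), and the triggering event is kept.

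| k | s | All events | Stop at first qualifying event | Double counting |
|---|---|---|---|---|
| 1.7 | 0.5 | 0.671 | 0.690 | 0.671 |
| 1.7 | 1 | 0.663 | 0.697 | 0.663 |
| 1/1.7 | 0.5 | 0.692 | 0.733 | 0.689 |
| 1/1.7 | 1 | 0.681 | 0.734 | 0.681 |

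Treating the qualifying change as a counted terminal event gives almost the same ratios as the stopping column (0.690, 0.698, 0.730, 0.733). At s = 1, stopping cuts events from 325 to 192 (41%) and from 297 to 154 (48%). That is somewhat less than the closed form, which ignores terminal events.

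**The case against.** The strongest reply is that Table 3 is written in the language of a maintenance regimen. Row 2 compares an effective dose with a baseline dose and cites ACE inhibitors and beta-blockers, and row 1 cites long-term drugs. That is probably the intent. But the examples do not limit the rule, and the operative words in row 2 are "for any class of medication that is part of a subject's baseline medication regimen".

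A second reply is that counting intensification as worsening is deliberate, since SAP 4.1 opens with progression of heart failure. That is a defensible choice of estimand. It still does not justify scoring an admission and its treatment as two events, or mixing a diuretic course with adoption of a new drug class.

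Three stronger readings might be inferred, and the documents do not support them:
- *Every heart failure hospitalization qualifies as an intervention.* The endpoint definition needs no 100% increase and can be met by mechanical therapy, ultrafiltration or paracentesis. In-hospital doses may never be recorded. The COVID form began only in April 2020, by which time about 60% of expected events had occurred (SAP 7). The CEC Charter, which supersedes the protocol definition, was not available. Inclusion criterion 5 is an eligibility rule and does not establish that every subject takes a diuretic.
- *The primary result is at risk.* Table 3 feeds only sensitivity analyses and one supporting win ratio. In SAP 5.6 it is the last tier, reached only when a pair ties on hospitalizations, so the effect there is small.
- *Confounding by new drugs goes untested.* SAP 5.2 truncates follow-up at 6, 12 and 24 months for that reason and does not use Table 3. The device rows 3 to 5 and 8 are also untouched.

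**Conclusion.** The point stands as a stated rule that misfires in supportive analyses. Followed literally, rows 1 and 2, and through them rows 6 and 7, can score treatment of a decompensation as an intervention, and nothing in SAP 4.1 prevents double counting. The primary test, alpha and power are unaffected.

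The losses of 45 to 55% and the total of 582 are upper bounds for changes made at the event: they assume that every first event, or every non-terminal event, triggers the rule and is recorded. They also keep the triggering event. SAP 4.1 does not say whether an admission on the censoring date counts, and a diuretic doubling recorded before admission would remove that admission too.

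On the rate ratio the effect is modest. Stopping at the first qualifying change pulls it towards 1, from about 0.66-0.69 to 0.69-0.73. Double counting leaves it almost unchanged but inflates the count and reduces the weight of terminal events, from 18% to as little as 10% of the total.

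**What to change.** Amend SAP 4.1 and Table 3:
1. Define rows 1 and 2 on non-diuretic heart failure drug classes. Report diuretic intensification as its own row, and show rows 6 and 7 with and without it.
2. Do not treat a drug change that starts and ends within an adjudicated endpoint event as an intervention. Date a change that continues after discharge from the discharge date.
3. In the event-counting analyses, count an endpoint event and the drug change made to treat it once.

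Two tighter rules are tempting but would do harm. Requiring a change to persist to the next scheduled visit makes qualification depend on later survival and attendance, over intervals of up to 180 ± 60 days (Protocol Table 6). Excluding all parenteral drugs would discard ongoing parenteral therapy, which is a real intensification.

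The cost is one extra table row, SAP wording and some programming; no change in data collection is proposed. The downside is that drug changes confined to an endpoint event no longer qualify as interventions.

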### 3.12. Withdrawal of a Subject

A subject may be withdrawn or partially withdrawn from the trial at any time by the investigator for a variety of reasons including, but not limited to, the subject not following trial-related directions, or a serious reaction develops or implantation of the BAROSTIM NEO System in countries where the device is market approved. A subject may also choose to voluntarily withdraw consent for the trial or from receiving further trial treatment at any time. The subject’s eligibility for continuing medical care will not be affected by his/her withdrawal from the trial.

The investigator should discuss the decision with the subject and clearly document the reason, date of discussion and who participated in the discussion along with the items discussed in the subject’s medical record. Note the non-US PIs will make every effort to encourage the subjects to stay in the trial to their assigned randomization before opting out to a BAROSTIM NEO implant.

Should a subject express the desire to withdraw from the study, the subject should be made aware of the option to partially withdraw from the study. This may be done through a consent form for subjects who wish to discontinue active follow-up in the trial, but not fully withdraw. The objective of the partial withdrawal is to allow site personnel continued access to subject medical records in order to collect information for the morbidity and mortality endpoint. Please refer to Section 3.4.5 Partial Withdrawal

For subjects who progress in their heart failure status to receive either a cardiac assist device or a heart transplant, see Section 3.15.

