#### **5.6. Win Ratio Expanded – HF Therapy**

A Win Ratio analysis will be performed using the components of the morbidity and mortality endpoints as well as intensification of therapeutic interventions for heart failure. This analysis will follow the same methodology as the Win Ratio above. The following hierarchy will be used:

4. CV Death
5. Heart transplant or LVAD
6. Number of hospitalizations for Heart Failure
7. Intensification of therapeutic interventions for heart failure as defined in Table 3.

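### In SAP 4.1 (event-counting analyses of Table 3 rows 5, 6 and 8) and the last tier of SAP 5.6, a BAROSTIM implant that in practice only controls can have counts against the control arm

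*SAP*

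**What the plan says.** SAP 4.1 addresses therapy added during follow-up. Table 3 has eight rows. Row 5 reads "Intervention is defined as non-protocol implantation of a BAROSTIM NEO device". Row 6 combines rows 1-5 and row 8 combines rows 3-5, so both contain row 5. The SAP then states: "The sensitivity analyses defined below will be performed for each of the additional therapeutic interventions in Table 3". There are four such analyses:

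1. Censor at the first intervention: "the earliest occurrence of the specified therapeutic intervention will NOT be considered an event contributing toward the endpoint".
2. Treat the intervention as a terminal event: "For this sensitivity analyses, these terminal events will be considered as an event contributing toward the endpoint".
3. Count everything: "An analysis that counts all specified therapeutic interventions as events contributing toward the endpoint, with follow-up time accruing until last available contact/death".
4. Impute events after the intervention, separately by arm. The imputed events count; the text does not say that the intervention itself does.

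The win ratio in SAP 5.6 has as its last tier "Intensification of therapeutic interventions for heart failure as defined in Table 3", with no exception for row 5.

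Three other places bear on this. SAP 4.4 describes crossover for medical management subjects only. Protocol 3.12 lists among possible reasons for withdrawal "implantation of the BAROSTIM NEO System in countries where the device is market approved", and asks non-US investigators to encourage subjects to stay in their assigned arm first. In the primary analysis (SAP 3.1.1) a BAROSTIM implant in a control is neither an endpoint event nor a censoring point.

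**The concern.** Counting added therapy as a failure is a fair stress test when subjects in both arms can receive that therapy. Rows 1-4 (new drug class, dose increase, CRT, CardioMEMS) meet this condition. Row 5 does not: a device-arm subject has BAROSTIM by protocol and has no matching event to score. Each control who obtains the device adds an event to the control arm, whether or not heart failure had progressed, because row 5 requires no sign of progression. In SAP 5.6 the same implant can turn a tied pair into a win for the device.

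SAP 4.1 presents these analyses as a way to gauge how much bias added therapy introduces. For row 5, and for the row 5 part of rows 6 and 8, analyses 2 and 3 introduce a bias of their own, always in the device's favour. The SAP carries no caveat. At stake is the reading of robustness results and of a supporting win ratio; SAP Section 5 says that its analyses are meant to support labeling.

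**Working it through.** **Plan's own figure.** The SAP gives no crossover count and no operating characteristics for these analyses, so there is no stated figure to reproduce. The SAP's conditional power and type I error concern the primary test and are not in dispute here.

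**Which analyses are affected**

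| Analysis | Row 5 implant scored as an event? |
|---|---|
| 1. Censor | No, by express statement |
| 2. Terminal event | Yes, in rows 5, 6 and 8 |
| 3. Count all | Yes, in rows 5, 6 and 8 |
| 4. Imputation | Not stated to count; imputed events do |
| SAP 5.6, last tier | Scored as intensification |
| Primary analysis | No |

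Rows 1-4 and 7 do not contain row 5. Four subjects randomized to treatment were never implanted (SAP Section 1) and could in principle receive a non-protocol implant, but they lie outside the 319 analysed.

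**Inputs for the size**
- Analysis population 319 (SAP Section 1) and 1:1 allocation (Protocol 3.1): 319/2 ≈ 160 controls. The final split is not given.
- 320 events at the final analysis (SAP Section 2). With no true effect: 160 per arm.
- Crossovers x: not in the documents. Assumed at 2%, 5% and 10% of 160, that is 3, 8 and 16.

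**Count-all analysis, row 5, no true effect.** Follow-up time is unchanged, so the rate ratio is RR = 160/(160 + x):
- x = 3: 160/163 = 0.98
- x = 8: 160/168 = 0.95
- x = 16: 160/176 = 0.91

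The result depends little on follow-up length. Using the protocol's expected 2.3 years (Protocol 4.3.3) and 0.4 events per patient-year (SAP 8.1) in both arms instead gives 319 × 2.3 × 0.4 = 293 events, about 147 per arm, and 147/(147 + 16) = 0.90 at the largest x.

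**Rows 6 and 8.** If rows 1-4 (or 3-4) add m events to each arm, the count-all ratio becomes (160 + m)/(160 + m + x), which is closer to 1. In the terminal-event version of these rows, a crossover adds an event only if it is the subject's first listed intervention. The proportional tilt is therefore largest in row 5 itself.

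**Simulation check, row 5.** Settings: N = 319, control rate 0.4, SAP dispersion 1.7 read as a gamma shape, assumed uniform follow-up of 1 to 4 years, negative binomial fit without covariate or other terminal events. The yardstick is one-sided rejection at a nominal 2.5%. No true effect, crossover at a random time, 1,500 runs per setting:

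| Controls crossing | Censor | Count all | Terminal event |
|---|---|---|---|
| 2% | RR 1.00, 2.1% | RR 0.98, 3.3% | RR 0.98, 3.5% |
| 5% | RR 1.00, 2.0% | RR 0.95, 5.5% | RR 0.94, 7.1% |
| 10% | RR 1.00, 2.3% | RR 0.90, 11.0% | RR 0.88, 15.1% |

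The terminal-event version tilts more because it also removes the control's later follow-up time. If crossover instead follows a first event (700 runs), 5% and 10% crossover give 0.95 and 0.91 for count-all and 0.93 and 0.87 for terminal-event.

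With a true ratio of 0.65 and random crossover of 5% and 10% (400 runs), count-all gives 0.625 and 0.60, terminal-event 0.61 and 0.57, and censoring 0.65 in both. The primary analysis gives 0.66 and 0.665, slightly diluted.

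**Win ratio.** No figure can be given. The last tier is reached only by pairs tied on all earlier tiers, and it also takes in rows 1-4.

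**The case against.** The strongest reply is that nothing decisive rests on these analyses. Success depends only on the primary Z-statistic crossing its boundary (SAP 3.1.4), and no rule in SAP 4.1 turns the sensitivity results into a claim of robustness. Versions free of the problem are already planned: row 5 has its own censoring and imputation analyses, SAP 4.4 censors controls when device therapy is turned on, and the intention-to-treat analysis in SAP 4.3 adds no crossover event. A reader will see the counting versions beside these. The counting rule also has a rationale, namely that progression leads to added therapy, and it is applied uniformly to every row.

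Most of this stands as a limit on importance. It does not make the counting versions sound for row 5: a uniform rule is not neutral when one arm cannot have the event, and an unbiased companion analysis does not correct a biased one.

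A reader might infer that the Table 3 analyses as a whole are tilted. They are not: two of four analyses on three of eight rows are affected, plus one win-ratio tier. A reader might also infer that the protocol expects controls to cross over in numbers. Protocol 3.12 only allows for it and asks non-US investigators to discourage it, and the no-charge device for US controls comes only after the study has ended (Protocol 3.1). Crossover may therefore be rare.

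**Conclusion.** The concern holds in a limited form. In the terminal-event and count-all analyses of rows 5, 6 and 8, and in the last tier of SAP 5.6, a BAROSTIM implant scores against the control arm and in practice cannot score against the device arm. The direction is certain; the size is not. For row 5 under no true effect, the count-all ratio moves to about 0.98, 0.95 or 0.91 with 3, 8 or 16 crossovers, and the terminal-event ratio somewhat further. Below about 2% of controls the tilt is small. These figures rest on an assumed crossover count, an even split of 319 subjects and 160 events per arm.

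It would be wrong to conclude that the primary result or its type I error is biased. Crossover is not an event there, and a crossover left in the primary analysis tends to dilute a true effect.

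**What to change.** - In SAP 4.1, state that BAROSTIM implantation is not counted as an endpoint event in any analysis.
- For row 5, keep only the censoring and imputation analyses.
- In the event-counting versions, count rows 1-4 for row 6 and rows 3-4 for row 8, and relabel those versions so that the narrower set is plain.
- In SAP 5.6, exclude row 5 from the last tier.
- Report the number of non-protocol BAROSTIM implants by arm beside all of these results, so that readers can judge the scale.

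The cost is SAP wording and a small programming change. Within rows 6 and 8 the event-counting versions would cover fewer interventions than the censoring versions, so the four analyses of a row would no longer address the same set. In the counting versions a crossover subject stays in the assigned arm with no adjustment for the device received. Some supportive results may become slightly less favourable to the device. If the sponsor prefers to keep the counting versions as they are, the minimum is to label them as one-sided in favour of the device and give the crossover counts by arm.
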